9.8.4. Sequence of analyses

Five separate data collection activities are planned for this study. First, structured data will be collected for all eligible patients and will be used to classify patients into the cohorts defined in Section 9.3. Chart review will then be undertaken in a sample of 100 front-line alectinib patients. As chart review data become available, analyses will be undertaken to meet the study objectives in Phase 2.

During Phase 3, all eligible patients for structured data and a sample of additional patients for chart review as defined by the cohorts specified in Section 9.3.1 will be identified. Structured data collection and chart review will occur simultaneously. Analyses to meet study objectives will occur after chart review is complete. No interim analysis is planned.

All eligible patients for the Phase 3 exploratory analysis as defined by the criteria in Section 9.3.2 will be identified and analyses to meet the exploratory objectives will occur after the main objectives are complete.

9.9. Quality control

For structured data, Ontada's Real World Research team conduct quality assurance checks on all analytics projects. The process includes both technical and clinical quality checks. Technical review of the dataset consists of identifying inappropriate values (e.g., out of range, illogical), logical sequences and quantity of missing values. Illogical and missing data will be reported to the study team, which may opt to exclude or impute these values. Clinical review of the data subsequently occurs to ensure aggregate data are aligned with expectations and prior publications.

The quality assurance process includes the following areas:

- Project scope and study rules
- Protocol development
- Data extraction and integrity
- Populated tables and study report development

As results of quality assurance and quality control, we confirm:

- The source of the data and/or results will be documented, and that results/data will be verified against the source
- The internal consistency of the medical research data presented
- The conclusions are objective, balanced and consistent with the study results
- The format and content of the document are aligned with the agreed upon template and standards

Quality control and validation of chart review (unstructured) data will occur in multiple phases. Prior to full chart review, a pilot will be conducted with at least 5% of the patient population, up to 25 patients. Charts will be reviewed by each reviewer on the team to ensure inter-rater reliability. Data Collection Manager/Team Lead will review pilot data for accuracy and consistency, including implausible dates (i.e., date of death prior to last date of treatment), non-standard treatments, results which are inconsistent with known clinical parameters or other clinical data which is inconsistent with known standards and outcomes. Chart review team will meet following pilot and before launch of full chart review to clarify ambiguous or conflicting data and address potential problems and questions. Pilot data will be presented to the research team for review and approval. If necessary, revisions to the tool and/or additional training will be implemented.

Once the pilot chart review is complete, the remaining chart reviews will proceed. During this phase of chart review, Data Collection Manager/Team Lead will perform random and detailed checks of the data by verifying original source data. The Data Collection Manager will also initiate queries, Quality Control (QC) of randomly selected charts and review of final data set before submission to researcher. Finally, the researcher and study's statistical lead will provide a final examination of the final dataset by looking for missing or illogical data before preparing it for analyses. This analysis will include a descriptive analysis of the provider characteristics, demographics, baseline clinical and disease characteristics, and characteristics of treatment patterns. Data points flagged as outliers will be reviewed by the Chart Review Team Lead.

Based on extensive experience with chart abstraction of real-world oncology data, the Ontada Life Sciences team has created chart abstraction guidelines to reflect best practices in data collection across a number of disease areas.[24] The intent of this document is to ensure accurate, objective and consistent data capture.

9.10. Limitations of the research methods

9.10.1. Internal validity of study design

Measurement error(s)/misclassification(s)

This observational and retrospective study uses iKM EHR data. The iKM database is not collected for research purposes but for clinical practice reasons. This may impede the standardization of the data collection methods and instruments and the reporting practices of the physician. As with all administrative databases, iKM data are subject to coding errors of omission and commission. Problems with inadequate or inaccurate codes in the databases may introduce some level of misclassification bias of certain diagnoses, events, or procedures of interest in the study. Likewise, some variables of interest may not be as complete across the entire population. The iKM EHR contains information on patients only when they are seen by US Oncology Network physicians. Services and procedures provided outside of The US Oncology Network are not captured by the database, as well as drugs received by patients from pharmacies not affiliated with US Oncology Network practices.

A patient's treatment history prior to his/her first encounter at a US Oncology Network practice may be only available in physician progress notes and is not well captured in the iKM EHR. We cannot rule out the possibility that some patients coded as receiving being treatment naïve for advanced disease in iKM EHR actually had previous chemotherapy or other treatment for advanced disease in healthcare facilities outside The US Oncology Network.

Information bias

Due to the nature of the study design, there is potential for bias to be introduced into the calculations of clinical outcomes. Specifically, patients who received treatment during the patient identification period may be meaningfully different from other patients who received therapy prior or after the study identification period.

Confounding

The iKM system is used for clinical practice reasons, not solely for research purposes. As such, associations but not causality can be detected, thus bias may be introduced by confounding factors. For example, data may be collected with an intent-to-treat approach, meaning based on when treatment is assigned rather than received. In particular, it will not be possible to determine if oral therapies were dispensed or taken; therefore, we'll use an intent-to-treat approach for analysis, with the assumption that all prescribed oral therapies were taken. Likewise, patients who do and do not receive the treatment at one point in time may be fundamentally different than those who received treatment during the observation period. These confounding factors are most likely to affect the outcomes being considered for this estimation study.

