² Patients with ongoing alectinib treatment, patients who discontinued alectinib and patients who did not have a subsequent treatment may be analyzed as separate cohorts depending on sample size of patients

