9.2. Study Design Phase 3 (study refresh and exploratory analysis)

During the Phase 3 data refresh, patients who have evidence of receiving alectinib during 01 June 2017 and 31 August 2020 will be eligible for inclusion in the study. Patients will be followed longitudinally until 31 August 2021, last patient record or date of death, whichever occurs first.

An overview of the study design for Phase 3 is presented in Figure 2.

Figure 2. Phase 3 data refresh study design

^{*}Last visit = last physical encounter, X = Additional visit or record of death

Phase 3 structured data objectives will be assessed among patients who meet study eligibility criteria as specified in 9.3.1 and stratified by subsequent treatment following alectinib.

Cohort A: All alectinib treated patients (overall population)

Cohort B (Alectinib only cohort): Alectinib treatment ongoing, or discontinued and no subsequent treatment³

Cohort C: Alectinib followed by treatment X (top 3 most frequent)

Cohort D: Alectinib followed by treatment Y (top 3 most frequent)

Cohort E: Alectinib followed by treatment Z (top 3 most frequent)

[figure not shown]
³ Patients with ongoing alectibin treatment, patients who discontinued alectinib and patients who did not have a subsequent treatment may be analyzed as separate cohorts depending on sample size of patients

Two groups of patients are planned for chart review during Phase 3. The first group includes patients from Phase 2 chart review who had ongoing treatment at the end of the observation period (31 December 2019). These patients will undergo additional follow-up through 31 August 2021.

An additional sample of approximately 100 patients who meet the Phase 3 eligibility criteria and received alectinib as front-line therapy and received subsequent treatment among the following groups will also undergo chart review:

- Alectinib → lorlatinib
- Alectinib → crizotinib
- Alectinib → brigatinib
- Alectinib only
- Alectinib → chemotherapy (optional)

Figure 3. Phase 3 exploratory analysis study design

^{*}Last visit = last physical encounter, X = Additional visit or record of death

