9.6. Study size

A preliminary feasibility assessment for Phases 1 and 2 identified 293 patients who were treated with alectinib after 01 November 2017, with approximately half treated in the front-line setting. Of the 293 patients receiving alectinib, 74% (n=217) patients had an ALK result. Approximately 20-30% of the 293 patients received a subsequent therapy after alectinib. It is estimated that approximately 300 patients will be included in the Phase 2 structured data analysis. Targeted chart review for Phase 2 is proposed to occur on 150 patients receiving alectinib to identify at least 100 patients who received alectinib as front-line. In the event the total number of eligible patients following structured data screening exceeds the planned number of charts for review, a random sample will be selected.

For Phase 3 structured analysis, a preliminary feasibility assessment identified 521 patients who were treated with alectinib from 01 June 1 2017 through 31 December 2020. Chart review for Phase 3 will include patients who had ongoing treatment at the end of Phase 2

study period, and an additional 125 patients will be targeted to identify 100 new patient who received alectinib as front-line therapy. For Phase 3 exploratory analysis, a preliminary feasibility assessment identified 134 patients who were treated with lorlatinib from 01 November 2018 through 31 December 31 2020.

The final study population for analysis will be defined after identification and review of the patient population meeting the eligibility criteria in the iKM database. A specific power calculation will not be performed as this is a descriptive analysis.

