9.8.1. Analysis sets

Phases 1 and 2

For analyses performed to meet the Phase 1 objectives, all patients who the meet the eligibility criteria defined in Section 9.3.1 will be considered. The study cohorts will be identified based on subsequent therapy following alectinib. For these analyses, datasets consisting of the structured data elements, plus the LADMF to confirm vitality status, required for the landscape analyses will be constructed.

The Phase 2 (chart review) analyses will be limited to a sample of 100 qualified front-line alectinib patient charts identified from Phase 1. The chart review analysis sets will be constructed from both structured and unstructured data, with the LADMF used to confirm vitality status.

Phase 3

For analyses performed to meet the Phase 3 unstructured objectives, all patients who the meet the eligibility criteria defined in Section 9.3.1 will be considered. The study cohorts will be identified based on subsequent therapy following alectinib. For these analyses, datasets consisting of the structured data elements, plus the LADMF to confirm vitality status, required for the landscape analyses will be constructed.

Phase 3 chart review analyses will include a subset of patients from Phase 2 chart review who had ongoing treatment at the end of the observation period and an additional sample of 100 qualified front-line alectinib patients from Phase 3. The chart review analysis sets will be constructed from both structured and unstructured data, with the LADMF used to confirm vitality status.

Some data elements will be captured with both structured and unstructured data. Since the chart review data are expected to provide a richer source of information, if data are available from both sources for a single patient, then chart review data will supersede what is available in the structured iKM data for the final analysis. To account for this, a final analysis data set will be constructed and used to update the landscape analyses once chart review data are available.

For Phase 3 exploratory analysis, all patients who meet the eligibility criteria defined in Section 9.3.2 will be considered. The study cohorts will be identified based on subsequent therapy following lorlatinib. For these analyses, datasets consisting of the structured data elements will be constructed.

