9.8.3. Statistical methods

Description of study enrollment

To be included in the study patients must meet each of the inclusion criteria and none of the exclusion criteria listed in Section 9.3.1. Counts of patients excluded for each criterion will be summarized.

Additionally, the counts of patients to be classified into the following subgroups will be presented⁵:

- Cohort A: All alectinib treated patients (overall population)
- Cohort B (Alectinib only cohort): Alectinib treatment ongoing, or discontinued and no subsequent treatment⁶
- Cohort C: Alectinib followed by treatment X (top 3 most frequent)
- Cohort D: Alectinib followed by treatment Y (top 3 most frequent)
- Cohort E: Alectinib followed by treatment Z (top 3 most frequent)

Description of patient demographic, clinical and treatment characteristics

Descriptive analyses will be conducted to evaluate the demographic, clinical and treatment characteristics overall, as well as for each of the study cohorts. Results will be reported in

⁵ Final cohorts will be decided upon sample size. Patients receiving chemotherapy after initiating alectinib will be included in the patient sample

⁶ Patients with ongoing alectibin treatment, patients who discontinued alectinib and patients who did not have a subsequent treatment may be analyzed as separate cohorts depending on sample size of patients

aggregate. Categorical variables (e.g., ECOG performance status) will be reported as frequency and percentage. Continuous variables such as age will be reported as mean, standard deviation, median and range (minimum-maximum). In the case of missing observations, the number and percentage of missing values will be reported.

For comparative analysis, i.e. comparing 2 or more treatment groups (e.g., ALK inhibitor sequences) or strata (front-line alectinib and non front-line alectinib), statistical significance will be reported with level of statistical significance based on p = 0.05 level as well as 95% confidence intervals.

Chi-square testing will be used to assess associations between categorical variables when patient counts for single cells within the results tables are greater or equal to 5. When distribution cannot be assumed to be Chi-square, then Fisher's exact test will be used. Depending on normality, Analysis of variance (ANOVA)/t-tests or Kruskall-Wallis tests will be used for continuous variables. An alpha level of 0.05 will be the primary criterion for statistical significance of this study.

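### A patient who stops alectinib and leaves the network can only be counted as having no subsequent treatment, so the post-alectinib share is understated to the extent that next treatments go uncaptured.

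*Combined protocol and SAP*

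**What the plan says.** Under measurement error, Section 9.10.1 states that "The iKM EHR contains information on patients only when they are seen by US Oncology Network physicians". Services given elsewhere are absent, "as well as drugs received by patients from pharmacies not affiliated with US Oncology Network practices". Under confounding, the same section adds that "it will not be possible to determine if oral therapies were dispensed or taken", and it treats a prescribed oral drug as taken.

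Section 9.8.1 sets the allocation rule: "The study cohorts will be identified based on subsequent therapy following alectinib". Section 9.2 gives "Cohort B (Alectinib only cohort): Alectinib treatment ongoing, or discontinued and no subsequent treatment", and Sections 9.1 and 9.8.3 say the same in substance. A footnote to Section 9.1, repeated in Sections 9.2 and 9.8.3, allows the component groups to be separated, but only as an option: they "may be analyzed as separate cohorts depending on sample size of patients". No group exists for an unknown next treatment.

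The plan does expect patients to be lost. In Table 1 (Section 9.4), a patient without a documented stop date, including one lost to follow-up, receives the earliest of the final treatment date, death date or study end. Section 9.3.1 requires only two visits after index date-1, with no minimum spacing.

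Under Section 9.8.3, cohort sizes are counts and categorical results are frequencies and percentages. DOT, OS and PFS use Kaplan-Meier with censoring at the last visit or study end, and OS and PFS are compared by log-rank tests. Section 9.8 rules out a separate SAP. Section 9.6 reports the feasibility result: "Approximately 20-30% of the 293 patients received a subsequent therapy after alectinib".

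**The concern.** What follows alectinib is the core question (objectives 2 and 6). A patient who stops alectinib, moves care and starts another ALK inhibitor elsewhere leaves no trace of that drug in iKM. The cohort scheme then has only one place for this patient, the stopped part of Cohort B.

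Two results are affected. The reported share with a next treatment is too low by whatever was not captured. And the alectinib-only group, which is described in the tables and compared on OS and PFS, mixes patients known to have had nothing further with patients whose next treatment nobody could see. Section 9.10.1 applies the outside-care gap to treatment before the first encounter. It does not carry it forward to treatment after alectinib.

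**Working it through.** **1. Tracing the patient who leaves.** Outside care is not recorded (Section 9.10.1). The last treatment date can stand as the stop date for a patient lost to follow-up (Table 1). Cohorts are assigned from the subsequent therapy found (Section 9.8.1). With no later record, the patient fits only "Alectinib treatment ongoing, or discontinued and no subsequent treatment" (Section 9.8.3). The time-to-event outcomes stop counting this patient at the last visit; the cohort count does not.

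**2. The plan's own figures.** 217/293 = 74.06%, which reproduces the 74% with an ALK result in Section 9.6. The 20-30% is an empirical count with no formula, so it cannot be rebuilt. In patients, 0.20 × 293 = 58.6 and 0.30 × 293 = 87.9 have a next therapy, leaving 234.4 and 205.1 in Cohort B.

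**3. Effect of non-capture.** Let s be the observed share and c the probability that a next treatment is captured. Then true share = s/c, patients wrongly in Cohort B = 293 × (s/c − s), and inflation of Cohort B = (1 − s)/(1 − s/c) − 1. No value of c is given, so the range is assumed. Each cell runs from s = 20% to s = 30%.

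| Assumed c | True share | Patients misplaced | Inflation of Cohort B |
|---|---|---|---|
| 0.95 | 21.1% to 31.6% | 3.1 to 4.6 | 1.3% to 2.3% |
| 0.90 | 22.2% to 33.3% | 6.5 to 9.8 | 2.9% to 5.0% |
| 0.80 | 25.0% to 37.5% | 14.6 to 22.0 | 6.7% to 12.0% |
| 0.70 | 28.6% to 42.9% | 25.1 to 37.7 | 12.0% to 22.5% |

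For scale: if the 58.6 to 87.9 treated patients split evenly over Cohorts C to E (an assumption), each holds 19.5 to 29.3, so 90% capture misplaces about a third of one such cohort.

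**4. Effect on the treatment mix.** With true oral share m among next treatments, observed oral share = m·c_oral / (m·c_oral + (1 − m)·c_infused). Take m = 70% as an illustration.
- Equal capture leaves it at 70%.
- c_oral = 0.70 and c_infused = 0.95: 0.49/(0.49 + 0.285) = 63.2%.
- c_oral = 0.95 and c_infused = 0.80: 0.665/(0.665 + 0.24) = 73.5%.

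The mix is biased only if capture differs by drug, and the bias can go either way.

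**5. Reach of chart review.** About 100 of an expected 300 patients are charted in Phases 1 and 2 (33%). In Phase 3, at most about 100 + 100 = 200 of 521 are charted (38%), leaving 321/521 = 62% on structured data alone. These Phase 3 figures are approximate, because the 521 were counted to 31 December 2020 while identification ends on 31 August 2020.

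**The case against.** The strongest reply is that this is a disclosed and unavoidable limit of a single-EHR descriptive study, and that the plan already works against it. Chart review is there to confirm oral ALK inhibitor data (Section 8). Table 1 draws subsequent treatments from structured data and charts. Chart data override structured data and update the landscape analyses (Section 9.8.1). Loss to follow-up is an abstracted reason for stopping, and Cohort B may be split. All this is true and reduces the problem. It does not remove it: the charts cover a front-line sample, they belong to the same EHR and show outside therapy only if a note mentions it, the lorlatinib analysis uses structured data only, and the split is optional and has no unobservable group.

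A reader might infer more than the documents support:
- That a written rule codes a missing record as no treatment. None exists; it follows from the cohort definitions.
- That an error rate applies to all of Cohort B. For example, 5-15% of 205 to 234 gives 10 to 35 patients. But patients still on alectinib have no next drug to miss, so that base is too large.
- That the overall error runs one way. Non-capture does. But counting every prescribed oral drug as taken can raise the share, so the net direction is not fixed.
- That the three most frequent next treatments are shifted towards drugs handled in the network. No difference in capture by drug is shown, and outside infusions are lost too.
- That Section 9.10.1 contradicts itself on pharmacies and prescriptions. The pharmacy sentence can be read as concerning dispensing, with prescriptions as the exposure record. The wording needs clarifying, because a drug prescribed in the network and filled elsewhere is captured on one reading and lost on the other.

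**Conclusion.** The point holds for patients who stop alectinib and are not seen again. The plan gives them no category of their own, counts them as having no subsequent treatment, and reports the post-alectinib share without the censoring that it uses for its other outcomes.

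The size is unknown. Under assumed capture of 95% down to 70%, about 3 to 38 of 293 patients are misplaced and a reported 20-30% corresponds to 21-43%. At high capture the effect is small. These figures assume that the feasibility share carries over, that capture does not vary between patients, and that chart review corrects nothing; they also leave out drugs prescribed but not taken. No direction can be given for the treatment mix. This is an inexpensive improvement to a central result and does not invalidate the study.

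**What to change.** 1. **Make the split of Cohort B mandatory** in Sections 9.1, 9.2 and 9.8.3: ongoing at data cut-off; stopped and still seen in the network with no next treatment; died with no next treatment; and stopped with no later network contact, labelled as next treatment not observable. Define the last group by a visit window fixed in advance, and apply it only to patients with at least that much time before data cut-off. Those who stop later are administratively censored. Apply the window also to deaths long after the last visit, since the LADMF records deaths that occur after a patient has left the network.
2. **Report the share starting each next treatment as cumulative incidence**, censored at the last iKM visit or data cut-off, with death as a competing event, beside the crude percentages. State the time origin: Table 1 uses the start of the next therapy when a stop date is missing, so a clock starting at the end of alectinib gives those patients a gap of zero.
3. **State in Section 9.5 and Table 1** that any iKM prescription, order or chart note counts as treatment whatever pharmacy dispensed it, and align the two statements in Section 9.10.1.
4. **Use the charted patients** to estimate how many next treatments the structured data miss, and give a sensitivity range for the share. This also helps with patients who keep attending but obtain a drug elsewhere, whom the window cannot detect.

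The cost is protocol wording, some extra categories, one table and one comparison, from data already planned. Cohort B becomes smaller, and the window length is arbitrary. The cumulative incidence assumes that censoring at the last visit is non-informative, which fails if patients leave because they are switching treatment; state this as a limitation.
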